1. SUMMARY

Coronavirus disease 2019 (covid-19) was classified as a pandemic by the WHO in March 2020. The SARS-COV-2 virus is easily transmissible and there is currently no approved treatment with effective results. Although the main epidemiological parameters are currently being studied, apparently the rate of contagion, incidence and mortality rate in severe cases seems to be high. For this reason, there is an urgent need to find a viable therapeutic option. Trying to respond to this need, the objective of this study is to determine the efficacy of standard treatment reinforced with two doses repeated in two consecutive days of plasma from people convalescing from the COVID-19 disease already discharged and / or with results in negative COVID-19 detection tests, transfused to hospitalized COVID-19 patients, both from the COVID-19 plant and from the ICU of HUSLL **and their counterparts in the participating centres**, who meet the inclusion criteria and sign the informed consent to participate in the study. To this end, a pilot study of an open-label, phase I, **multicentre**, open-label clinical trial will be carried out to study the efficacy of strengthening conventional therapy with passive immunization through repeated infusion of plasma compared to exclusive standard treatment in COVID-19 **patients**. The study will be led by the **Son Llàtzer University Hospital**, which has designed the project and will act as a coordinating centre. For the evaluation of efficacy, both clinical, immunological and safety criteria will be collected. It is expected to have results in a short period of time from the approval of the corresponding ethics committees.

2. BACKGROUND AND JUSTIFICATION

The first cases of COVID-19 date back to December 31, 2019, when the Wuhan Municipal Health and Sanitation Commission (Hubei Province, China) reported on a group of 27 cases of pneumonia of unknown ethiology, with a common exposure at a wholesale seafood, fish and live animal market in Wuhan City, including seven severe cases [1]. The first case, recorded on December 8, 2019, began with the following symptoms: fever, dry cough, dyspnoea and radiological findings of bilateral pulmonary infiltrates [2]. A month later, on January 7, 2020, the Chinese authorities identified as the causative agent of the outbreak a new type of virus of the *Coronaviridae* family that has subsequently been named SARS-CoV-2, whose genetic sequence was shared by the Chinese authorities on January 12 [3]. The disease caused by this new virus has been referred to by international consensus and the WHO as COVID-19 [4].

As it is a pandemic that has affected the whole world at all social levels, the WHO offers a series of reports with updated information, almost daily, with the numbers of cases (classified by infections, deaths, discharged, among others), both globally and classified by countries, can be consulted at (https://www.who.int/docs/default-source/coronavirus/situation-reports/20200413-sitrep-84-covid-19.pdf?sfvrsn=44f511ab_2). The data consulted on April 14, 2020 (when the initial version 1.0 study was designed) indicated that globally there were: total confirmed cases: 1,773,084, total new confirmed cases: 76,498, total deaths: 111,652, total new deaths: 5,702. In Spain total confirmed cases: 169,496, total new confirmed cases: 4,167, total deaths: 16,972, total new deaths: 619 [5]. According to data from the Spanish Ministry of Health, in the Balearic Islands there were a total of 1,571 infected of which died: 117, cured: 862 (<https://covid-19.isciii.es/>). As of July 23, 2020, when the study becomes multicentre, and according to the daily report of the WHO (https://www.who.int/docs/default-source/coronavirus/situation-reports/20200722-covid-19-sitrep-184.pdf?sfvrsn=7680210a_2) [6], worldwide there are a total of confirmed cases: 14,765,256 (since the beginning of the pandemic), total of new confirmed cases per day: 202,726, total deaths: 612,054 (since the beginning of the pandemic). pandemic) and 4,286 new ones per day. In Spain total confirmed cases: 267,551 (since the beginning of the pandemic), total of new confirmed cases: 730 in one day, on July 22, total deaths: 28,426 [7].

People infected with COVID-19 are known to experience immunological and physiological changes that fundamentally affect the airways [8]. At the pathophysiological level, the following symptoms are the most frequent: at the systemic level: fever, cough, fatigue, headache, diarrhoea, hypoxemia, involvement of the cardiac system, lymphopenia, among others. At the level of the respiratory system: pneumonia, acute respiratory distress syndrome [9].

As for its transmission in a span of a few months, COVID-19 has become a pandemic due to its transmissibility, spreading across all continents with a notable daily increase in the number of cases and deaths [10]. Although most infected people exhibit mild illness (80%+), 14% have severe illness and 5% have critical illness. Approximately 10% will require hospital admission, of which approximately 10% will require ICU care, including invasive ventilation due to acute respiratory distress syndrome (ARDS) [11]. While mortality appears to be more common in older people and people with comorbidities, such as chronic lung disease, cardiovascular disease, and diabetes, young people without comorbidities also appear to be at risk of progressing into multi-organ failure and death [12]. There have been a growing number of studies published rapidly online and in academic journals; however, some of these may be of limited quality and are published preliminarily without sufficient review. Therefore, a critical evaluation of existing studies is needed to determine whether the existing evidence is sufficient to support the management strategies currently proposed.

There are several therapeutic approaches to COVID-19 disease: antiviral compounds that inhibit enzymatic systems, those that inhibit the entry of SARS-CoV-2 into the host cell, acting on the mechanisms of interaction between the host and the pathogen, and finally immunomodulators that are supposed to reduce the cytokine storm and associated lung damage. As for therapies, little is known so far about how to definitively treat this disease, in the sense that many laboratories worldwide are working both to improve the detection of the disease and to create a vaccine. It should be noted that no drug is approved by international agencies for COVID-19. The time needed to complete this type of research is much slower than the speed with which the pandemic worsens, so at the moment the main therapies reported in the scientific literature are limited to the use of some antivirals and drugs such as: chloroquine, arbidol, remdesivir and favipiravir. Existing in some articles with tables summarizing the main agents with potential efficacy in the treatment of SARS-CoV-2 (see [13]). A metanalysis observational studies on passive immunotherapy for SARS and severe forms of influenza indicates a decrease in mortality, but the studies were of low or very low quality and lacked control groups [14]. In Middle East Respiratory Syndrome (MERS), the use of fresh frozen convalescent plasma or immunoglobulins from recovered patients has been discussed [15]. Patients recovered from SARS develop a neutralizing antibody response [15]. Preliminary data indicate that this response also extends to SARS-CoV-2 [16]. Others have argued that plasma from convalescent donors could be an option for the prevention and treatment of COVID-19 disease. In a preliminary series of uncontrolled cases of 5 critical patients with COVID-19 and ARDS, administration of plasma from convalescent COVID-19 donors containing neutralizing antibodies was accompanied by an improvement in their clinical status [17].

There are further examples where convalescent plasma has been successfully used as post-exposure prophylaxis and/or treatment of infectious diseases, including other coronavirus outbreaks (e.g., SARS-1, MERS). Convalescent plasma has also been used in the COVID-19 pandemic; limited data

from China suggest a clinical benefit, including radiological resolution, reduced viral loads and improved survival. Globally, blood centres have a robust infrastructure for conducting collections and building inventories of convalescent plasma to meet growing demand. However, there are major challenges, both regulatory and logistical, encompassing donor eligibility, donor recruitment, collections, and transfusion itself including dose study. Data from rigorously controlled clinical trials of convalescent plasma are also few, underscoring the need to evaluate its use objectively for a range of indications (e.g., prevention versus treatment) and patient populations (e.g., age, disease, comorbidity)[18][19][20]. The joint application of immunotherapy with immune IgG antibodies combined with antiviral drugs as an alternative treatment against COVID-19 has also been studied until more definitive options such as vaccines are available [21]. Therefore, while promising, plasma from convalescent donors has not yet been shown to be safe and effective as a treatment for COVID-19. The effect of strengthening retroviral therapies combined with immunotherapy is also not known exactly [21]. The scientific community indicates that a careful clinical evaluation with this type of therapy should allow to quickly establish whether such passive immunotherapy, administered in the early stages of the disease in patients at high risk of harmful evolution, can reduce the frequency of patient deterioration and, consequently, mortality from COVID-19 [22][23]. Therefore, it is important to study the safety and efficacy of COVID-19 convalescent plasma in clinical trials. In this sense, the present study aims to determine the efficacy of reinforcing standard treatment with infusions of repeated doses of plasma from patients convalescing from the COVID-19 disease already discharged and / or with results in the negative COVID-19 viremia tests, in COVID-19 patients still hospitalized, comparing it with the results obtained with the exclusive standard treatment that is being used in patients infected by COVID-19. Therefore, to evaluate the immunological efficacy of the reinforcement of standard treatment with hyperimmune plasma vs standard therapy without reinforcement.

In April 2020, version 1.0 of this study was designed, which was approved by the corresponding committee and funded by the Health Research Institute of the Balearic Islands in June 2020. In July 2020 due to the context of the increase in the number of infected after the confinement and foreseeing a possible scenario of increase in cases in the coming months, different health centres in the Balearic Islands requested HUSLL to be part of the study, so version1.0 adapts and is presented in this document for implementation as a multicentre study.

3. HYPOTHESIS AND OBJECTIVES

3.1. Hypothesis:

Plasma from people who have been infected and have overcome the COVID-19 disease is expected to have sufficient and compatible levels of antibodies (anti-COVID-19) to neutralize the viral load that a person infected and still convalescing with COVID-19 may present. Therefore, it is expected that the efficacy of the reinforcement of standard therapy with repeated transfusion of immune plasma from COVID-19 convalescents vs standard therapy alone in hospitalized COVID-19 patients will be more effective at the therapeutic level and may be a possible palliative until the discovery of a vaccine. Mitigating the inflammatory phase of the disease and therefore reducing the risk of ARDS.

3.2. Objectives

3.2.1. Main objective:

The objective of the study is to determine the efficacy of reinforcing standard treatment with repeated infusions of plasma from people ex-convalescent of COVID-19 disease (already discharged and/or with negative COVID-19 test results), transfused to COVID-19 patients still hospitalized, both COVID-19 plant and HUSLL ICU ([and collaborating centres participating in the multicentre study](#)). Comparing it with the results obtained with the exclusive use of standard treatment, which is being used in patients infected with COVID-19. Therefore, to assess the immunological efficacy of the reinforcement of standard treatment vs standard therapy without reinforcement.

3.2.2 Secondary objectives:

Secondary objectives are related to evaluating not only efficacy at the clinical level, but also tolerance, safety and immunological aspects. Below is a list of the main secondary objectives:

- To assess the serological response to Coronavirus SARS-CoV-2 in patients with plasma transfusion and compare it with patients who have received treatment standard.
- Analyse the influence of the number of antibodies of the donor on the clinical evolution of the recipient.

-Analyse the efficacy of the experimental treatment that will reinforce the standard treatment, comparing it with the exclusive standard treatment at the level of the main clinical parameters during and after the treatment.

-To assess the safety of experimental reinforced treatment, comparing it with standard treatment during and after treatment.

-To assess the tolerance of experimental reinforced treatment, comparing it with standard treatment during and after treatment.

-Evaluate the feasibility of the experimental reinforced treatment.

-To assess the virological response of patients with plasma transfusion versus patients with standard treatments.

-Find if there is a certain patient profile where this therapy is most effective, either by age group, blood group, sex, or presence/absence of other pathologies.

-On the contrary, determine if there is a certain profile of patients (as in the previous case) in which the treatment is less effective.

-To know retrospectively the parameters of antigenemia and viral load of convalescent patients infected by COVID-19.

-Find possible weak points of experimental therapy that need to be studied to be improved in future studies.

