darunavir/cobicistat; remdesivir), interferon- α/β , anti-IL-6 monoclonal antibody (Tocilizumab) or oxygen therapy among others. The ratio controls: treated will be 1:2 in favour of the treatment. As treatments have been changing throughout the pandemic, when performing the final analysis, a stratified analysis will be made by type of treatment. That is, infected patients who have been treated with the same drugs will be compared.

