4.3.1. Stages of study and evaluation of the response

a) The study procedures for the patient receiving treatment shall be carried out as follows:

1. Baseline visit/screening:

- Review of inclusion and exclusion criteria: HIP and CI signature.
- Vital signs: Blood pressure, Heart rate, Respiratory rate, Temperature, and oxygen saturation.
- Complete physical examination.

- Review of relevant medical history.
- Rx of Tx
- Electrocardiogram.
- Weight, height, Body mass index.
- ECOG.
- Complete hematology.
- Coagulation study, D-dimer.
- Arterial blood gas.
- Biochemical analysis: Glucose, creatinine, glomerular filtration (CKD-EPI), sodium, potassium, chlorine, or rhea, urate, calcium, ferritin, C-reactive protein, AST, ALT, GGT, FA, LDH, CPK, troponin, procalcitonin.
- Inflammatory parameters: IL-6.
- Serology HIV, HVC, HVB, SYPHILIS.
- Imaging tests according to usual practice.
- Real Time-PCR for detection of Coronavirus SARS-COV-2 in nasal smear and pharynx.
- Quantitative determination of antibodies (IgG, IgM) against Coronavirus SARS-COV-2.
- Immunohematological study (ABO Group, Rh, Indirect Coombs).
- Concomitant medication evaluation.

2. Treatment initiation visit (First dose: day 1): Marked procedures (*) do not need to be repeated if performed at baseline in the previous 7 days:

- Study treatment assignment: if it is an intervention group, first plasma infusion.
- Vital signs (TA, FC, FR, T^a) pre-infusion and post-infusion*.
- Complete physical examination*.
- ECOG*.
- Hematology*.
- Biochemical analysis*.
- Inflammatory parameters*.
- Concomitant medication evaluation.
- Evaluation of emerging adverse effects.

3. Visit of Day 2:

- if it is an intervention group, second plasma infusion.
- Concomitant medication evaluation.
- Evaluation of emerging adverse effects.

4. Visit of Day 3:

- Vital signs (TA, FC, FR, T^a).

- Physical examination.
- ECOG.
- Hematimetry.
- Biochemical analysis.
- Inflammatory parameters.
- Nasal and pharyngeal smear for RT-PCR of Coronavirus SARS-COV-2.
- Quantitative determination of antibodies (IgG, IgM) against Coronavirus SARS-COV-2.
- Concomitant medication evaluation.
- Evaluation of emerging adverse effects.
- Clinical/virological response evaluation.

5. Visit of Day 7:

- Vital signs (TA, FC, FR, T^a).
- Physical examination.
- ECOG.
- Hematimetry.
- Biochemical analysis.
- Inflammatory parameters.
- ECG.
- Nasal and pharyngeal smear for RT-PCR of Coronavirus SARS-COV-2

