- Quantitative determination of antibodies (IgG, IgM) against Coronavirus SARS-COV-2.
- Concomitant medication evaluation
- Evaluation of emerging adverse effects.
- Clinical/virological response evaluation.

6. Visit of Day 14:

- Vital signs (TA, FC, FR, T^a).
- Physical examination.
- Hematimetry.
- Biochemical analysis.
- Nasal and pharyngeal smear for RT-PCR of Coronavirus SARS-COV-2.
- Quantitative determination of antibodies (IgG, IgM) against Coronavirus SARS-COV-2.
- Concomitant medication evaluation.
- Evaluation of emerging adverse effects.
- Clinical/virological response evaluation.

7. Visit of Day 21/end of study (at discharge):

- Vital signs (TA, FC, FR, T^a).
- Physical examination.

- Rx of Tx to assess evolution/resolution of infiltrates.
- ECG.
- ECOG.
- Hematimetry.
- Biochemical analysis.
- Inflammatory parameters.
- Real Time-PCR for SARS-COV-2 viral load study.
- Quantitative determination of antibodies (IgG, IgM) against Coronavirus SARS-COV-2.
- Concomitant medication evaluation.
- Evaluation of emerging adverse effects.
- Clinical/virological response evaluation.

IMPORTANT: In cases where the patient is discharged after 7 days, visits on day 14 and day 21 can be made on an outpatient basis, in outpatient consultations or day hospital, after appointment with the patient.

Screening visits and day 1 may overlap on the same date threaten life the inclusion criteria are confirmed and none of the exclusion is met.

There will be a margin of +/- 24 hours to perform the procedures of visits 7, 14 and 21 (to be able to adjust the appointments in external consultation).

The study procedures for study subjects (control and treatment groups) can be reviewed in summary form in the following table:

Procedure	Study days						
	Screening/ Basal	Day 1*	Day 2	Day 3	Day 7	Day 14	Day 21
DATE							
Signature of informed consent	X						
Medical history review	X						
Physical examination	X	X*		X	X	X	X
Vitals signs	X	X*		X	X	X	X
Weight, Height, BMI	X						
ECOG	X	X*		X	X	X	X
ECG	X				X		X
ABO/Rh Group	X						
Hematimetry	X	X*		X	X	X	X
Coagulation	X	X*		X	X	X	X
Biochemistry	X	X*		X	X	X	X
Study of inflammatory parameters	X			X	X		X
Serology Important IgG/IgM anti-COVID	X			x	x	x	x
Quantitative titration antibodies	X			X	X	X	X
COVID PCR	X			X	X	X	X
Chest Rx	x						x
AE Review	X	X	X	X	X	X	X
Concomitant review	X	X	X	X	X	X	X
Clinical response	X			X	X	X	X
PLASMA TRANSFUSION		X	X				

Table 3. Summary of procedures in the study subjects.

LEGEND:

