5. DATA ANALYSIS: STATISTICS

A descriptive analysis of all variables will be performed. With the categorical variables, the global percentages and frequencies will be estimated. Normality tests and graphs will be used to determine if the quantitative variables follow a normal distribution. Normal distribution variables shall be expressed as mean \pm standard deviation and those without normal distribution shall be expressed as median and interquartile range. To describe the significance and associations between variables after the intervention, parametric and non-parametric tests will be used as appropriate (the student's t test of paired samples or the Wilcoxon test for quantitative variables and the ANOVA test for paired samples or Friedman test for qualitative variables). The correlations will be examined by the correlation of Spearman or Pearson ranges and a multivariate analysis will be performed to assess the effect of other factors such as the confusion/interaction effect, as well as to assess the possible construction of predictive models. A p-value $< 0,05$ shall be considered an indicator of a significant difference. SPSS v.23 software will be used for data analysis.

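### Recipient antibody is measured before plasma in both arms but is not named as a covariate or effect modifier, so a benefit concentrated in antibody-negative recipients would be diluted and could be missed

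*Combined protocol and SAP*

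**What the plan says.** - **Rationale (3.1).** Donor plasma is expected to carry "sufficient and compatible levels of antibodies (anti-COVID-19) to neutralize the viral load" in the recipient.
- **Measurement (4.3.1).** The screening visit includes "Quantitative determination of antibodies (IgG, IgM) against Coronavirus SARS-COV-2". The schedule in Table 3 is introduced with "The study procedures for study subjects (control and treatment groups) can be reviewed in summary form in the following table", and both serology and quantitative titration are marked at Screening/Basal. The variable list in 4.3.3 holds the titre as a number in UA/mL.
- **Responder factors (3.2.2).** The profile of patients in whom plasma works best is to be sought "either by age group, blood group, sex, or presence/absence of other pathologies". The companion objective, on patients in whom it works less well, refers back to the same list.
- **Roles given to antibody (3.2.2).** The donor's level is a planned predictor: "Analyse the influence of the number of antibodies of the donor on the clinical evolution of the recipient". The recipient's level appears as an outcome: "To assess the serological response to Coronavirus SARS-CoV-2 in patients with plasma transfusion", compared with standard treatment.
- **Analysis (section 5 and 4.1).** Section 5 says "a multivariate analysis will be performed to assess the effect of other factors such as the confusion/interaction effect" and names no factor, model or outcome. The tests it does name are for paired samples. Section 4.1 adds that "a stratified analysis will be made by type of treatment", which refers to background drugs.
- **Eligibility and assignment (4.2.1, 4.2.2, 4.1).** No recipient criterion uses serostatus. The nearest is a limit of 7 days from symptom onset, for ward and ICU alike. Assignment is simple randomisation without stratification by serostatus, and patients recruited while plasma is out of stock go to control.

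**The concern.** The treatment is a passive supply of antibody. Whether a recipient already has antibody is therefore a natural candidate for deciding who gains, and the trial measures it before treatment. The plan leaves it without a role on the baseline side of any analysis.

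Two things are at stake. First, if the effect is larger in antibody-negative recipients, a single pooled comparison averages it with a smaller effect in the others. Second, titre is itself an outcome, so its baseline value is the most obvious covariate for it. Without adjustment, a baseline difference between arms remains in the follow-up comparison. Such a difference can arise by chance under unstratified assignment, or systematically, because stock-out patients enter control without randomisation. A serostatus analysis chosen after the results are known, in an open-label trial, would carry little weight.

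**Working it through.** The plan states no sample size, power or effect size, so there is no figure to reproduce. What follows is an illustration.

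**Inputs from the documents:** significance level 0.05 (section 5; two-sided assumed). Section 4.1 gives allocation both as equiprobable and as 1:2 control to treated. These statements must be reconciled, and both ratios are used here.

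**Assumed inputs:** antibody-negative share f from 0.3 to 0.9; standardised effect d = 0.5 or 0.8 in antibody-negative recipients and 0 in the rest; SD 1; total N of 50, 100 or 200; 80% power for the sample sizes. N = 100 only echoes the remark in 4.2.10 that the coordinating hospital had fewer than 100 COVID-19 inpatients when version 1.0 was written.

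**Dilution.** Pooled effect = f × d. Required N scales as 1/(f × d)², so the multiplier is 1/f². At f = 0.8 this is 1/0.64 = 1.56; at 0.7, 1/0.49 = 2.04; at 0.5, 1/0.25 = 4.00.

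**Power at N = 100, 1:1 (50 per arm), d = 0.5, f = 0.7:**
- Overall test: Φ(0.35 × √(50/2) − 1.96) = Φ(−0.21) = 42%.
- Antibody-negative subgroup, 35 per arm: Φ(0.5 × √(35/2) − 1.96) = Φ(0.13) = 55%.
- Interaction: SE = √[(1/50 + 1/50) × (1/0.7 + 1/0.3)] = 0.436; Φ(0.5/0.436 − 1.96) = Φ(−0.81) = 21%.

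Results for d = 0.5. The undiluted total N is 126 (1:1) or 144 (1:2). The power columns are for N = 100, 1:1.

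| f | Pooled effect | N multiplier | Total N, 1:1 / 1:2 | Overall | Antibody-negative subgroup | Interaction |
|---|---|---|---|---|---|---|
| 0.9 | 0.45 | 1.23 | 156 / 177 | 61% | 66% | 11% |
| 0.8 | 0.40 | 1.56 | 198 / 222 | 52% | 61% | 17% |
| 0.7 | 0.35 | 2.04 | 258 / 291 | 42% | 55% | 21% |
| 0.5 | 0.25 | 4.00 | 504 / 567 | 24% | 42% | 24% |
| 0.3 | 0.15 | 11.11 | 1396 / 1572 | 11% | 28% | 21% |

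Over all the assumed inputs, power of the overall test runs from about 7% (f = 0.3, d = 0.5, N = 50, 1:2) to over 99% (f = 0.9, d = 0.8, N = 200). At d = 0.8, N = 100 and f = 0.7 it is 80% (1:1) or 75% (1:2).

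**Baseline imbalance.** If follow-up log titre depends on baseline with slope β, the unadjusted arm difference contains β × (baseline difference). At N = 100, 1:1, the chance baseline difference has SD √(1/50 + 1/50) = 0.20 baseline SDs, so a 95% range of ±1.96 × 0.20 = ±0.39. The documents give no β. The unadjusted standard error already allows for chance imbalance, at a cost in precision. It does not allow for differences brought in by the stock-out rule.

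**The case against.** - **A missed benefit is not shown.** A reader might infer that a benefit in antibody-negative recipients would be missed. The documents do not support that: with N, effect size and seropositive share all unstated, power in the illustration runs from about 7% to over 99%. This objection stands; the benefit could be missed.
- **The protocol does not say that antibody-positive recipients gain little.** Section 3.1 speaks of donor antibody neutralising the recipient's virus and of mitigating inflammation. It says nothing about the recipient's own antibody. This stands too: a concentrated benefit is a plausible inference, and zero effect in antibody-positive recipients is a simplifying assumption.
- **The 7-day symptom limit selects early disease.** It may raise the antibody-negative share and so reduce dilution. By how much is unknown, and it is a proxy for something the trial measures directly.
- **Baseline antibody is not excluded.** A reader might take the four listed factors as closed and section 5 as ruling the variable out. Section 3.2.2 presents its list as the main secondary objectives, and section 5 leaves confounding and interaction open. The variable is unspecified, as is every other covariate, and that is the defect that pre-specification repairs.
- **The remedy is weak on power.** The interaction test reaches at most about 24% at N = 100 and d = 0.5, and a main-effect covariate does not undo dilution. Both are true. The gain is adjusted comparisons and interpretable estimates by serostatus, not a confirmatory test.

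**Conclusion.** The omission is confirmed. Recipient antibody is quantified before plasma in both arms, yet it is not named as a covariate or responder factor, and the multivariate analysis that could use it is unspecified.

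If benefit is confined to antibody-negative recipients, dilution follows by arithmetic: a sample-size multiplier of 1.56 to 4 for an assumed antibody-negative share of 80% down to 50%. Whether the trial would then fail to see the benefit cannot be determined from the documents. The imbalance argument is independent of that assumption and is strongest for titre, plausible for PCR. Adjustment for baseline titre would remove only the part of any stock-out difference that runs through baseline titre.

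This is a pre-specification point of moderate weight in a pilot trial, worth acting on because the data are already being collected.

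**What to change.** **Section 5.** State that the between-arm comparisons of titre, PCR and clinical outcomes are adjusted for baseline IgG, on the log scale, with a stated rule for values below detection. Take baseline from the last pre-infusion sample, and from the corresponding pre-day-1 sample in controls. Antibody is not on the day 1 schedule and screening need not fall on day 1, so record the sample date.

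**Section 3.2.2.** Add baseline serostatus as a pre-specified exploratory effect modifier. Report the arm effect with a confidence interval in each serostatus group, together with an arm-by-serostatus interaction. Define serostatus by the assay's positivity cut-off and name the assay. The only antibody threshold in the protocol, 50 UA/mL, is for donors, and a common recipient assay across centres is not stated.

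**Cost.** Some wording, one derived variable and a little more analysis; no new visit or sample. The subgroup and interaction estimates will be imprecise and should be labelled exploratory. The covariate deals with imbalance and precision; only the serostatus-specific estimates and the interaction address dilution.
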